## Clinical Protocol FIH-3

Doc No: CLINP1837  
Revision: D  
DCO No: 25-009  
Effective Date: 02/06/25

B-Mode Ultrasonography During Amplifi System Treatment (by Investigator)		X	X 		
Contrast Venography (by Investigator)		X	X 	X	
Concomitant Medications		X	X	X	X
Adverse Event Logging		X	X	X	X
Determination of Study AVF Maturation (Y/N)					X
Documentation of unplanned stoppages, malfunction and deficiencies		X	X	X	
Documentation of Study AVF Thrombosis Events, Interventional Procedures, and Surgeries					X
Documentation of Access-Related Thrombosis Events, Interventional Procedures, and Surgeries (all types of access)					X

1. For Subjects that experience a prolonged Pump stoppage only
2. ACT measurements during Amplifi System placement and AVF creation per Amplifi System IFU
3. Daily testing

**Table 4: Time Windows for Study Assessments**

Assessment	Time Window 
Baseline Screening Ultrasonography	≤14 days prior to planned Amplifi System placement
Inclusion and Exclusion Criteria, Demographics and Medical History, and Informed Consent and HIPAA Authorization	≤14 days prior to planned Amplifi System placement
Baseline Clinical Assessment and Physical Exam	≤14 days prior to planned Amplifi System placement
Baseline Laboratory Testing	≤14 days prior to planned Amplifi System placement
Daily Ultrasonography During Amplifi System Treatment	Within 12-hour period of each day 
Daily Clinical Assessment and Physical Exam during Amplifi System Treatment	Within 12-hour period of each day
Daily Laboratory Testing During Amplifi System Treatment	Within 12-hour period of each day
Documentation of unplanned stoppages, malfunction, and deficiencies	Within 48-hour period of the time of event
Ultrasonography at the End of Amplifi System Treatment	≤4 hours prior to the planned end of treatment
Contrast Venography	During Amplifi System placement

## Clinical Protocol FIH-3

Doc No: CLINP1837  
Revision: D  
DCO No: 25-009  
Effective Date: 02/06/25

Assessment	Time Window 
	During Amplifi System removal and Study AVF creation surgery
Laboratory Testing after Study AVF Creation	±7 days
Clinical Assessment and Physical Exam after Study AVF Creation	±7 days
Study AVF Ultrasonography	±7 days for two (2) week ultrasonography ±2 weeks for six (6) week ultrasonography
Determination of Study AVF Maturation	±7 days for two (2) week ultrasonography ±2 weeks for six (6) week ultrasonography
Documentation of Study AVF Thrombosis Events, Interventional Procedures, and Surgeries	±7 days at 2 weeks ±2 weeks at 6 weeks
Documentation of Vascular Access-Related Thrombosis Events, Interventional Procedures, Surgeries (all types of access) 	±7 days at 2 weeks ±2 weeks at 6 weeks
Documentation of Hemodialysis Vascular Access-Related Hospitalizations (all types of access) 	±7 days at 2 weeks ±2 weeks at 6 weeks
Adverse Event Logging	Within 24-hour period of each day during Amplifi System treatment ±7 days at 2 weeks ±2 weeks at 6 weeks

1. Unless otherwise specified, times are measured from Study AVF creation date

2. Required

3. Does not include Study AVF

4. Includes Study AVF

## 8.1 Duplex Ultrasonography

### 8.1.1 Baseline Screening Ultrasonography

As shown in **Table 3**, Subjects will undergo screening duplex ultrasonography prior to enrollment and the results will be documented on the appropriate CRF. The protocol for the baseline screening duplex ultrasonography is summarized in **FIH3 Duplex Ultrasonography Protocol**. The patency, diameter, and blood flow of the veins of both upper extremities will be assessed, including the cephalic, basilic, median cubital, and perforator veins, to provide Investigators information to help them determine patient eligibility for the Study, choose potential locations for insertion of the Distal Outflow Catheter, and choose a planned location for Study AVF creation. The patency, diameter, and blood flow of the arteries of both upper extremities will be assessed, including the radial artery, to provide Investigators information to help them

## Clinical Protocol FIH-3

Doc No: CLINP1837  
Revision: D  
DCO No: 25-009  
Effective Date: 02/06/25

determine patient eligibility for the Study, and to choose a planned location for Study AVF creation. The patency, diameter, and blood flow of both internal jugular veins will be also assessed to provide Investigators information to help them choose potential locations for insertion of the Inflow Catheter, if needed.

Vein diameters will be measured in both the vertical and horizontal vessel dimension and artery diameters will be measured in the vertical dimension only, and reported in fraction of millimeters using digital calipers. A tourniquet will be applied at the proximal portion of the upper arm during assessment of upper extremity vein diameters. No tourniquet will be used during assessment of vein blood flow, and artery diameter and blood flow.

### 8.1.2 Ultrasonography During Amplifi System Treatment

Subjects will have limited ultrasonography at least daily to assess the patency and diameter of the cephalic vein in the middle third of the forearm. The protocol for ultrasonography during Amplifi System treatment is summarized in **FIH3 Duplex Ultrasonography Protocol**.

Vein diameters will be measured in both the vertical and horizontal vessel dimension. Amplifi System treatment will continue during this ultrasound examination and **tourniquet will be placed**. At the time of the first measurement post AVF creation, a mark will be made on the skin at the location of the first measurement using a permanent marker, and this mark will be used to make subsequent measurements.

Subjects that experience a prolonged Pump stoppage will have a duplex ultrasound examination of the treated upper extremity to evaluate patency of the upper extremity arm veins and identify any signs of injury, stenosis, occlusion, aneurysm formation, or intraluminal thrombus using the protocol for ultrasonography at the end of Amplifi System treatment, as summarized in **FIH3 Duplex Ultrasonography Protocol**. Sonographers will identify and record the location and extent of intraluminal thrombus present in the treated upper extremity after a prolonged Pump stoppage, if any, on the appropriate CRF. If no thrombus is identified, that will also be recorded on the CRF.

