**Clinical Protocol**  
**FIH-3**

Doc No: CLINP1837  
Revision: D  
DCO No: 25-009  
Effective Date: 02/06/25

PATIENT POPULATION	
Patients with end-stage renal disease (ESRD) and are currently receiving maintenance hemodialysis via a tunneled, cuffed hemodialysis catheter indicated for forearm radiocephalic AVF creation based on an Investigator's standard practice and have a wrist or distal forearm cephalic vein diameter of <math>\geq 1.7</math> mm and <math>\leq 3.2</math> mm at the proposed Study AVF creation.

EFFECTIVENESS MEASURES	
Percent change in cephalic vein diameter and blood flow in the middle third of the arm as measured by ultrasonography [Timeframe: from baseline, during Amplifi System treatment (minimum daily), and prior to Amplifi System removal and AVF creation]
 
Mean vein diameter of the cephalic vein and blood flow of brachial artery in the middle third of the forearm as measured by ultrasonography [Timeframe: 1, 2 and 6 weeks post AVF creation]
 
Forearm AVF maturation success at 2 and 6 weeks post-AVF creation [Timeframe: 2, 6 WK post AVF creation]
 
Percentage of subjects who experience an increase in the cephalic vein diameter of <math>\geq 2.7</math> mm from their baseline measurement, or an increase of <math>>1</math> mm from baseline, following treatment with the Amplifi System. [Timeframe: prior to removal of the Amplifi System and creation of the AVF].

SAFETY MEASURES	
Rate of Occurrence of Major Device-Related Adverse Events defined as: [Timeframe: from device implantation and up to 30 days from device removal and AVF creation]
 

• Amplifi System-related death;

• Amplifi System-related major bleeding, major pneumothorax, major air embolism, major thrombosis, major thromboembolism, major hemolysis, or major thrombocytopenia; localized infection

• Amplifi System-related re-hospitalization or prolonged hospitalization;

• Amplifi System-related major surgery or major interventional procedure; or

• any Amplifi System-related complication determined to be an Amplifi System-related major complication by both an Investigator and the Medical Monitor.

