## Clinical Protocol FIH-3

Doc No: CLINP1837  
Revision: D  
DCO No: 25-009  
Effective Date: 02/06/25

attached to the Inflow Access Port via a quick-connect (“Screw Lock”) fitting. The Distal Outflow Catheter tip is inserted into a vein in the upper extremity, with a taper to facilitate easy vein insertion. The Distal Outflow Catheter is joined to the Proximal Outflow Catheter using a connector (“Inline Connector”) and Screw Lock fittings. The proximal end of the Proximal Outflow Catheter can be trimmed to the appropriate length and attached to the Outflow Access Port via a Screw Lock fitting. During placement of the Amplifi System, the Pump is connected to the Controller via the integrated Pump cable. A control algorithm in the Controller automatically increases the speed of the Pump to maintain an elevated WSS in the cephalic vein as the treatment progresses and the cephalic vein dilates. During placement of the Amplifi System, the Blood Flow Sensor is connected to the Pump via the integrated Blood Flow Sensor cable.

Additional details of the Amplifi System can be found in the Investigator’s Brochure.

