#### 3.2.1 Device Performance Outcome

[figure not shown]
[figure not shown]
For both FIH1 and FIH2 the primary performance endpoint was the percent change in the treated cephalic vein diameter from baseline to the end of Amplifi System treatment. As shown in Figure 5, the cephalic vein diameter increased by 105% in FIH1 subjects and 150% in FIH2 subjects during the treatment period. As shown in Figure 6, mean imputed cephalic vein blood flow (as measured in the Proximal Outflow Catheter) increased 186% for FIH1 and 134% for FIH2 during the treatment period.

AVFs were successfully created with treated veins in all FIH1 and FIH2 subjects. As shown in Figure 5, for FIH1 subjects, mean AVF outflow vein diameter increased to 6.3 mm and mean AVF blood flow (imputed from brachial artery blood flow in some FIH1 subjects) increased to 851 mL/min six weeks after AVF creation (Figure 6). As shown in Figure 5 and Figure 6, for FIH2 subjects, mean AVF outflow vein diameter increased to 7.0 mm and mean AVF blood flow (imputed from brachial artery blood flow in all FIH2 subjects) increased to 1,153 mL/min six

weeks after AVF creation. There were no Amplifi System related or procedure-related serious adverse events.

[figure not shown]

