### 4.5 Primary Clinical Measures

#### Effectiveness Measures

- **Percent change in cephalic vein diameter and blood flow** in the middle third of the arm as measured by ultrasonography [Timeframe: from baseline, during Amplifi System treatment (daily), and prior to Amplifi System removal and AVF creation]
- **Mean vein diameter of cephalic vein and blood flow of brachial artery** in the middle third of the forearm as measured by ultrasonography [Timeframe: 1, 2 and 6 weeks post AVF creation]
- **Forearm AVF maturation success at 1, 2, 6 weeks post-AVF creation** [Timeframe: 1, 2, 6-WK post AVF creation]
- **Percentage of subjects who experience an increase in the cephalic vein diameter of  $\geq$ 2.7 mm from their baseline measurement, or an increase of  $>1$  mm from baseline, following treatment with the Amplifi System.** [Timeframe: prior to removal of the Amplifi System and creation of the AVF].

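### Percent change in cephalic vein blood flow by ultrasound conflicts with the daily scan plan, and its end-of-treatment value is confounded with pump output

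*Protocol*

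**What the plan says.** The synopsis lists, for both diameter and flow of the cephalic vein, a percent change "in the middle third of the arm as measured by ultrasonography [Timeframe: from baseline, during Amplifi System treatment (minimum daily), and prior to Amplifi System". Section 4.5 repeats the measure: "in the middle third of the arm as measured by ultrasonography [Timeframe: from baseline, during Amplifi System treatment (daily), and prior to Amplifi System removal".

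The assessment sections divide the work differently:

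- **Baseline (8.1.1).** Duplex covers patency, diameter and blood flow of the arm veins. A tourniquet is applied for vein diameters, but "No tourniquet will be used during assessment of vein blood flow".
- **During treatment (8.1.2).** The scan is described as "limited ultrasonography at least daily to assess the patency and diameter of the cephalic vein". Flow is not named.
- **End of treatment (8.1.3).** Duplex again covers patency, diameter and blood flow, at the baseline locations. Treatment continues during the scan and a tourniquet is on the treated arm, with no exception stated for flow.
- **Table 3.** It has a daily B-mode scan by the investigator, a general duplex row marked at every stage including Day 1–3, and a separate row for flow taken from recorded Amplifi System data on Day 0, Day 1–3 and at removal.

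On what drives flow, section 2.2 says "A control algorithm in the Controller automatically increases the speed of the Pump to maintain an elevated WSS in the cephalic vein", and ties this to the progress of treatment and dilation of the vein. On the earlier study, section 3.2.1 reports that "mean imputed cephalic vein blood flow (as measured in the Proximal Outflow Catheter) increased 186% for FIH1 and 134% for FIH2" over the time on treatment. Section 14.1 describes the effectiveness measure of the study as percent change in diameter only.

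**The concern.** There are two problems. First, the measure calls for ultrasound flow on each treatment day, but the section that defines the daily scan does not collect it. An analyst would have to leave those time points empty, use device-log values under an ultrasound label, or assume that the Table 3 duplex row includes flow.

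Second, the flow change that can be computed sets a vein at rest against a vein being perfused by the pump. Delivering flow is what the device does, so much of any rise would be the intervention itself. Listed as effectiveness, it could be read as a vein response. Because the study objective is to show outcomes similar to FIH, it could also be set beside the FIH flow figures, which are a different quantity.

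**Working it through.** The protocol states no figure for this measure, so there is nothing to reproduce. The check is a comparison of sections, followed by two short pieces of arithmetic.

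**Step 1. Source of flow at each listed time point**

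| Time point | Ultrasound flow in section 8.1 | Pump | Tourniquet | Other flow source (Table 3) |
|---|---|---|---|---|
| Baseline | Yes (8.1.1) | Not yet placed | Off for flow | None |
| Daily in treatment | Not named (8.1.2); duplex row marked in Table 3 | Running | On | Recorded device data |
| End of treatment | Yes (8.1.3) | Running | On, no exception for flow | Recorded device data |
| 1, 2, 6 weeks after AVF | Yes (8.1.4) | Removed | Off | None |

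Sections 8.1.1, 8.1.3 and 8.1.4 all name blood flow. Only 8.1.2 leaves it out, and Table 3 describes the daily scan as B-mode. Between baseline and end of treatment, pump state changes and, on the text as written, so does tourniquet state.

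**Step 2. What the computable change contains**

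Let Q0 be baseline flow without the pump, Q1 flow just after the pump starts, and Q2 flow at end of treatment with the pump running. Then

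Q2/Q0 = (Q1/Q0) × (Q2/Q1).

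The FIH-3 ultrasound measure is Q2/Q0 − 1. The first factor, Q1/Q0, is the effect of switching the pump on, before remodelling. The FIH flow change is read here as the second factor: a catheter flow does not exist before the pump runs, and section 3.2.1 reports the change over the treatment period. On that reading Q2/Q1 was 1 + 1.86 = 2.86 in FIH1 and 1 + 1.34 = 2.34 in FIH2. The two measures would agree only if Q1/Q0 were 1. The protocol gives neither Q0 nor Q1, so the gap cannot be sized. A tourniquet left on at the end scan could lower Q2, so the net direction is not fixed either.

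**Step 3. Does on-pump flow track dilation? (illustration)**

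Assume laminar flow, with wall shear stress proportional to Q/d³. Holding shear stress constant then requires flow to rise by the cube of the diameter ratio. Inputs are the cohort means in section 3.2.1.

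- FIH1: diameter ratio 1 + 1.05 = 2.05; 2.05³ = 8.62; observed flow ratio 2.86; 2.86/8.62 = 0.33.
- FIH2: diameter ratio 1 + 1.50 = 2.50; 2.50³ = 15.62; observed flow ratio 2.34; 2.34/15.62 = 0.15.

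FIH2 dilated more (150% against 105%) but had the smaller flow rise (134% against 186%). On-pump flow did not rank the cohorts as dilation did, which is consistent with flow being mainly pump output. This is only indicative: there were five subjects per cohort, a cubed mean ratio is not a mean of cubed ratios, and the diameter change runs from the pre-treatment baseline while the flow change covers the treatment period.

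**The case against.** A reader might infer that the measure cannot be computed at all. That goes too far: sections 8.1.1 and 8.1.3 both specify vein flow by duplex at the same locations, so the baseline-to-end change is available.

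A reader might also infer that every daily flow value is missing by design. The documents do not show that. Table 3 marks duplex for Day 1–3, section 8.1.2 defers to a separate ultrasonography protocol that is not shown, and device-recorded flow is scheduled throughout treatment. What stands is a contradiction about the source of daily ultrasound flow.

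A third tempting reading is that on-pump flow is a pure device setting and can show no effect. Section 2.2 says pump speed is raised as the vein dilates, so flow responds in part to dilation. Confounded is the right word. Nor do the documents support saying that any working pump guarantees a large increase, since they give no resting or on-pump vein flow.

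On the tourniquet, the sentence in 8.1.3 sits in the paragraph on diameters and may have been meant for diameters only. That is fair, but unlike 8.1.1 the section states no exception for flow. Settling this would still leave the pump-state difference.

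Finally, the study is descriptive, with up to ten subjects and no threshold resting on flow, and nothing commits the sponsor to comparing ultrasound flow with the FIH percentages. This limits the consequence. It does not remove the contradiction in a measure listed under the primary clinical measures.

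**Conclusion.** The point holds as an inconsistency between a listed effectiveness measure and its assessment plan, together with a confounded comparison at end of treatment. The size of the confounding is unknown because the documents give no unpumped or initial on-pump vein flow. The FIH cohort means suggest, without proving, that on-pump flow is a poor guide to dilation.

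The conclusion rests on reading 8.1.2 as a complete description of the daily scan and 8.1.3 as applying the tourniquet to the whole examination; the ultrasonography protocol could change either. It does not depend on that protocol for the pump-on against pump-off comparison, which follows from 8.1.1 and 8.1.3.

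The change is worth making but is not critical. Vein diameter, AVF maturation and brachial artery flow at 1, 2 and 6 weeks are untouched.

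**What to change.** - Reconcile the synopsis, section 4.5, Table 3 and sections 8.1.2 and 8.1.3 on the source of flow, its time points, and the pump and tourniquet state.
- Keep percent change in diameter as the treatment-period effectiveness measure, as section 14.1 already has it.
- Report treatment-period flow from the recorded Amplifi System data, start to end of treatment as in FIH, as a technical performance measure.
- If ultrasound flow at end of treatment is kept, label it on-pump flow, state the tourniquet condition, and do not present its change from baseline as effectiveness.
- Leave brachial artery flow after AVF creation as the effectiveness flow measure.

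The cost is protocol wording. The device flow data are already scheduled in Table 3, so no new collection is needed. The downside is that one favourable-looking effectiveness figure is lost.

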### 8.1.3 Ultrasonography at the End of Amplifi System Treatment

Subjects will have duplex ultrasonography at the end of the Amplifi System treatment period prior to Study AVF creation. The protocol for the ultrasonography after Amplifi System Treatment is summarized in **FIH3 Duplex Ultrasonography Protocol**. The patency, diameter, and blood flow of the veins of both upper extremities will be assessed at the same locations as the baseline screening duplex ultrasound examination.

Vein diameters will be measured in both the vertical and horizontal vessel dimension. Amplifi System treatment will continue during this ultrasound examination and **tourniquet will be placed on the treated arm**.

### 8.1.4 Ultrasonography of AVF

Subjects will have duplex ultrasonography of the Study AVF at 1, 2 and 6 weeks after Study AVF creation. The protocol for Study AVF duplex ultrasonography is summarized in **FIH3 Duplex Ultrasonography Protocol**. The patency, diameter, and blood flow of the arteries and veins of the upper extremity with the Study AVF will be assessed at the same locations as the

baseline screening duplex ultrasound examination. Vein diameters will be measured in both the vertical and horizontal vessel dimension and artery diameters will be measured in the vertical dimension only. **No tourniquet will be placed.**

## **8.2 Demographics and Medical History**

All Subjects will have demographics and a medical history recorded in the Study EDC System.

## **8.3 Clinical Assessments and Physical Exams**

Clinical assessments and physical exams, including vital signs and temperature, will be performed at screening, day 1 (prior to Amplifi System placement), and at the end of the Amplifi System treatment period. Assessments will be recorded in the Study EDC System.

## **8.4 Laboratory Assessments**

- A routine chemistry panel will be evaluated at baseline, at day 1 prior to Amplifi System placement, and at the end of Amplifi System treatment.
- A complete blood count (CBC) will be evaluated at baseline, on day 1 prior to Amplifi System placement, daily during the Amplifi System treatment period, at the end of Amplifi System treatment after Amplifi System removal, and 1, 2 weeks and 6 weeks after Study AVF creation. The baseline CBC results will be used to assess eligibility, the daily testing during the Amplifi System treatment period and the testing 1, 2 weeks and 6 weeks after Study AVF creation will be used to assess for hemolysis and anemia.
- PFH and LDH will be evaluated at baseline, on day 1 prior to Amplifi System placement, daily during the Amplifi System treatment period, at the end of Amplifi System treatment period after Amplifi System removal, and 1, 2 weeks and 6 weeks after Study AVF creation to assess for hemolysis.
- ACT will be evaluated during Amplifi System placement and removal, as per the Amplifi IFU, and during AVF creation, as per Standard of Care.

## **8.5 Contrast Venography**

The protocols for contrast venography are summarized in the **FIH3 Contrast Venography Protocol**. The Investigator performing each fluoroscopic, venographic, or angiographic study will document the findings on the appropriate CRF.

### **8.5.1 Venography Prior to Amplifi System Placement**

Contrast venography of the upper extremity, ipsilateral central veins, superior vena cava, and right atrium using an IV catheter *will* be performed for all Subjects prior to insertion of the Inflow Catheter or Distal Outflow Catheter evaluate patency of the cephalic vein, the draining veins of the upper arm, the ipsilateral central veins, the superior vena cava, and the right atrium.

Evaluating the veins of the arm by ultrasound is generally preferred to contrast venography. Ultrasound is generally inadequate in identifying subtle stenotic issues and flow pattern in the normal low flow state. It is also not adequate to visualize the central veins and right atrium, so contrast venography is needed to evaluate the patency of the central veins and right atrium prior to Amplifi System placement. If ultrasound is not available, or if the information obtained from an

